	
16. Known allergy and/or sensitivity to the test article or test article components;17. A condition that the investigator feels may put the subject at significant risk, may confound the trial results, or may interfere significantly with participation in the trial;18. Current enrollment in an investigational drug or device trial or previous use of an investigational drug or device within 30 days of Visit 1; 19. [REDACTED] 20. Current use of any medication known to cause ocular drying that is not used on a stable dosing regimen for at least 30 days prior to Visit 1; or21. Inability or unwillingness to follow instructions, including participation in all assessments and visits.
--	---

Evaluation Criteria:

Primary Endpoint:	Ocular discomfort symptom score (0 – 100 VAS) over 100 minutes in the CAE at Visit 1 and Visit 3
Safety Endpoints:	
• Visual acuity• Slit lamp examination• Adverse event query• Intraocular pressure

General Statistical Methods and Types of Analyses:

Statistical analyses will be detailed in the statistical analysis plan, which will dominate any statistical language herein. Any changes to protocol-stated analyses will also be detailed in the statistical analysis plan.

Sample Size:

[REDACTED]

[REDACTED]

[REDACTED]

[REDACTED]

Primary Efficacy Analysis:

The primary endpoint will be assessed using the intent-to treat (ITT) population with observed data only. The ITT population includes all randomized subjects.

Safety Analyses:

Safety endpoints will be summarized using descriptive statistics. For qualitative safety assessments, counts and percentages will be reported at the eye level and subject level, where appropriate. For quantitative safety assessments, endpoints will be summarized at the eye level using continuous summary statistics.

Summary of Known and Potential Risks and Benefits to Human Subjects:

Potential risks and benefits are described in the Investigator's Brochure.

TABLE OF CONTENTS

Clinical Trial Protocol: ADX-102-DED-032	1
SYNOPSIS	3
TABLE OF CONTENTS	8
List of Abbreviations	11
1 INTRODUCTION	12
2 STUDY OBJECTIVE	13
3 CLINICAL HYPOTHESES	13
4 OVERALL STUDY DESIGN	13
5 STUDY POPULATION	13
5.1 Number of Subjects (approximate)	13
5.2 Study Population Characteristics	13
5.3 Inclusion Criteria	13
5.4 Exclusion Criteria	14
5.5 Withdrawal Criteria (if applicable)	15
6 STUDY PARAMETERS	15
6.1 Primary Endpoint	15
6.2 Safety Endpoints	15
7 STUDY MATERIALS	16

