5.3 Inclusion Criteria

Each subject must meet each of the following criteria:

1. 18 years of age (either gender and any race);
2. Ability to provide written informed consent and sign the Health Information Portability and Accountability Act (HIPAA) form;
3. Reported history of ocular discomfort associated with dry eye disease for at least 6 months prior to Visit 1;
4. Reported history of use or desire to use eye drops for dry eye symptoms within 6 months of Visit 1;

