8.4 Early Termination/Discontinuation

If a subject is discontinued from the trial prior to Visit 3, then all safety evaluations that are to be performed at Visit 3 should be performed on the day of discontinuation (early termination) or at the discretion of the investigator.

Adverse events (both elicited and observed) and serious adverse events will be monitored throughout the trial. The investigator will promptly review all adverse events (both elicited and observed) for accuracy and completeness. All adverse events will be documented on the appropriate source document and case report form.

If a positive pregnancy test is observed during the trial, the investigator will notify [REDACTED] immediately. The investigator shall request from the subject and/or the subject's physician copies of all related medical reports during the pregnancy and shall document the outcome of the pregnancy. The investigator will retain the reports together with the subject's source documents and will provide a copy of all documentation to [REDACTED]. Pregnant subjects will be discontinued from the trial as per the exclusion criteria.

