9 ADVERSE EVENTS

9.1 Adverse Event

For the purposes of the trial, an adverse event is defined as any untoward medical event occurring after signing of the informed consent until exited from the trial. An adverse event can therefore be any unfavorable and unintended sign, symptom, or disease occurring after the subject started the clinical trial, without any judgment about causality. Any pre-existing medical condition that worsens during the trial will also be considered a new adverse event. Documentation regarding the adverse event should be made as to the nature, date of onset, end date, severity, relationship to study procedure, expectedness, action(s) taken, seriousness, and outcome of any sign or symptom observed by the investigator or reported by the patient upon indirect questioning.

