9.3.2 Reporting a Serious Adverse Event

To ensure subject safety, all serious adverse events, regardless of relationship to the test article, must be immediately reported. All information relevant to the serious adverse event must be recorded on the appropriate source

documents. The investigator is obligated to pursue and obtain information requested by [REDACTED] in addition to that information reported on the source document. All subjects experiencing a serious adverse event must be followed up and the outcome reported.

In the event of a serious adverse event, the investigator must notify [REDACTED] immediately; obtain and maintain all pertinent medical records, information, and medical judgments from colleagues who assisted in the treatment and follow-up of the subject; provide [REDACTED] with a complete case history; and inform the IRB of the adverse event within their guidelines for reporting serious adverse events.

Contact information for reporting serious adverse events:

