This SAP describes the data that will be analyzed to reveal subject characteristics, trial efficacy, and trial safety. Whereas the protocol presents a general discussion of statistical procedures, this SAP provides greater detail and further clarifies a particular application of a general procedure. Nevertheless, *in the event* of any discrepant directives between the protocol and the SAP, the SAP will supersede the protocol.

Additional analyses other than the planned analyses described herein may be conducted as ad-hoc analyses. All ad-hoc analyses will be identified in the CSR. The intent of any such analyses would be to better characterize treatment effects.

2. Summary of Statistical Deviations from the Protocol

Analyses outlined in this SAP are in all instances thought to be compatible with or complimentary to the more general presentation found in the protocol.

[figure not shown]
3. Trial Objectives

The general trial objective is to evaluate the efficacy of reproxalap in subjects with dry eye disease, as assessed by the primary endpoint of subject-reported ocular discomfort. As appropriate, these measurements occur prior to and after dosing, and within and outside a [REDACTED] (CAE).

4. Trial Variables

Efficacy and safety variables will be considered in what follows. The Schedule of Visits and Measurements that immediately follows summarizes the trial variables and conveys the trial's experimental design, including data collection time points. Together, the variables and experimental design provide a background context for the statistical hypothesis testing that is described later in this document.

Schedule of Visits and Measurements from Protocol

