17.1 Adverse Events

An adverse event is defined as any untoward medical occurrence associated with the use of an test article in humans, whether or not considered test-article-related. An adverse event can be any unfavorable and unintended sign (e.g., an abnormal laboratory finding), symptom, or disease temporally associated with the use of test article, without any judgment about causality. Exacerbation of conditions related to the signs and symptoms of dry eye disease will not be reported as an adverse event. The adverse event reporting period ends upon trial exit. Study drug includes the investigational drug under evaluation.

All adverse events will be coded using MedDRA Version 27.0 (or higher).

Treatment-emergent adverse events (TEAEs) are defined as any adverse event that occurs or worsens on or after the first dose of study treatment. Adverse events recorded in the eCRF which began prior to treatment will not be included in the summary tables but will be included in the adverse event data listings.

An overall summary will be presented that includes the number and percentage of subjects who experienced at least one AEs, ocular AEs, non-ocular AEs, SAEs, AEs by maximal severity, AEs by relationship to study procedure, AEs leading to treatment discontinuation, and AEs resulting in death by treatment arm for the Safety Population. In addition, overall TEAEs and the number and percentage of subjects who experienced at least one TEAE, ocular TEAEs, non-ocular TEAEs, TE-SAEs, TEAEs by maximal severity, TEAEs by relationship to study procedure, TEAEs leading to treatment discontinuation, and TEAEs resulting in death by treatment arm for the Safety Population.

Separate summaries will be provided for the following categories of AEs:

- Ocular AEs by SOC and PT
- Non-ocular AEs by SOC and PT

- Ocular TEAEs by SOC and PT
- Non-ocular TEAEs by SOC and PT
- Instillation Site Ocular TEAEs by Duration of Time
- Ocular TEAEs by SOC, PT, and maximal severity
- Non-ocular TEAEs by SOC, PT, and maximal severity
- Ocular TEAEs by SOC, PT, and strongest relationship to study procedure
- Non-ocular TEAEs by SOC, PT, and strongest relationship to study procedure
- Ocular TEAEs by SOC, PT, maximal severity, and strongest relationship to study procedure
- Non-ocular TEAEs by SOC, PT, maximal severity, and strongest relationship to study procedure
- TEAEs That Led to Premature Treatment Discontinuation
- SAEs

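### SAP 17.1 keeps dry-eye exacerbation out of adverse event reporting, Protocol 9.1 counts it as an adverse event, and the difference is neither declared nor bounded

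*SAP*

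**What the plan says.** Four pieces of text matter.

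- **Definition.** Protocol 9.1: "Any pre-existing medical condition that worsens during the trial will also be considered a new adverse event". It has no exception for dry eye. Inclusion criterion 3 (Protocol 5.3) requires "Reported history of ocular discomfort associated with dry eye disease for at least 6 months prior to Visit 1", so the disease under study is pre-existing in every eligible subject.
- **Recording.** Protocol 8.4: "All adverse events will be documented on the appropriate source document and case report form". Protocol 9.3.2 adds that "all serious adverse events, regardless of relationship to the test article, must be immediately reported".
- **Exclusion.** SAP 17.1, in the paragraph that defines an adverse event: "Exacerbation of conditions related to the signs and symptoms of dry eye disease will not be reported as an adverse event".
- **Precedence and declaration.** SAP Section 1 says that, where the documents differ, "the SAP will supersede the protocol". The protocol synopsis, under general statistical methods, promises: "Any changes to protocol-stated analyses will also be detailed in the statistical analysis plan". SAP Section 2, where such changes would appear, names none and calls its analyses "in all instances thought to be compatible with or complimentary to the more general presentation found in the protocol".

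**The concern.** A worsening of dry eye is an adverse event under one document and not under the other. Because the SAP prevails, the tables would follow the exclusion. The sentence does not say whether it limits recording, listings or tables. It does not define which conditions count as related to dry eye, and it makes no exception for serious events or for events that lead to discontinuation.

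At stake is the by-arm adverse event summary of one class of ocular event, in the treated organ and the studied disease: how many subjects had it, how severe and serious it was, how it was related to study procedures, and whether it led to stopping. The primary efficacy result is not affected.

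**Working it through.** The plan gives no figure to reproduce. The check sets the passages against a single test case: an enrolled subject whose dry eye worsens after the first randomized dose.

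1. **Classification.** Protocol 9.1 makes it a new adverse event. Protocol 8.4 requires it to be documented. Protocol 10.9 treats worsening after the first randomized dose as treatment-emergent and promises by-arm frequencies for treatment-emergent events, serious ones and those causing premature discontinuation. SAP 17.1 says it is not reported as an adverse event. The answers are opposite.

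2. **Which text governs.** For the analysis it is the SAP, by its Section 1 and by the protocol's own deference in the synopsis and in 10.4. That deference concerns statistical language and procedures. What sites record is set by Protocol 9.1 and 8.4, which the SAP does not expressly withdraw.

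3. **Whether it is declared.** The exclusion is visible in SAP 17.1 but is not identified as a departure from the protocol. SAP Section 2 has no entry for it. Since it changes the counts promised in Protocol 10.9, it falls within the synopsis commitment to detail changes to protocol-stated analyses.

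4. **What each reading would remove.**
   - *Tables only:* the event is missing from the ocular adverse event and treatment-emergent tables, and from the serious-event and adverse-event discontinuation tables where it belongs there. It stays in the subject listings that SAP 17.1 provides for all adverse events and serious adverse events.
   - *Tables and listings:* it is missing from both, but remains in the source documents and case report form.
   - *Recording as well:* it would never enter the database. No legible text tells sites to apply the sentence this way.

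5. **Where the boundary lies.** The legible text has no list of signs, symptoms or preferred terms. SAP 17.1 also tabulates instillation-site ocular events by duration, but no rule separates an instillation complaint from a dry-eye exacerbation. Similar complaints could be kept or dropped by judgement.

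6. **What remains in any case.** Serious-event notification (Protocol 9.3.2) stands. SAP Section 12 summarises reasons for trial discontinuation, and Protocol 10.4 has disposition presented by arm. Discomfort scores, slit-lamp findings and visual acuity are still reported by arm, though none of these carries seriousness or relationship.

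7. **Size.** Protocol Section 4 plans about 55 subjects per arm, so one subject is 1/55 = 1.8% of an arm. The documents give no rate for such events. For an assumed rate p, the chance of at least one affected subject among 110 is 1 − (1 − p)^110. This gives 42% at p = 0.5%, 67% at 1%, 89% at 2% and 99.6% at 5%. These rates are assumptions, and the result depends almost entirely on which is chosen.

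**The case against.** The strongest reply is that the exclusion has a sensible rationale. SAP 5.1 describes the CAE as a setting that brings out dry-eye symptoms, and Protocol 8.3.1 collects discomfort 16 times in each CAE exposure. Recording every provoked symptom as an adverse event would duplicate the endpoint and crowd the safety tables. This stands: including all dry-eye worsening in the adverse event tables is a debatable choice, and the documents do not compel it. The rationale supports a bounded, declared exclusion. It does not support one without limits or an exception for serious events.

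A second reply is that the precedence clause already settles the matter. It settles which text governs the analysis. It does not record that the analysis departs from the protocol, and it does not define the scope.

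A third is that redacted text, such as the severity definitions in Protocol 9.1.1 or Appendix 3, might hold an exception. That cannot be excluded, but the two conflicting sentences are legible and neither points to one.

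A reader might also infer more than the documents support:

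- *That these events will be irrecoverably lost.* This requires sites to apply an SAP sentence to data collection, while Protocol 9.1 and 8.4 still govern recording.
- *That discontinuations due to dry-eye worsening will disappear.* SAP Section 12 still counts them among the reasons for discontinuation, though perhaps without a dry-eye label.
- *That the excluded class is probably not empty.* This rests only on the assumed rate; at 0.5% the chance of any affected subject is below one half.

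**Conclusion.** The point holds as a contradiction between Protocol 9.1 and SAP 17.1 that is undeclared in SAP Section 2 and undefined in scope. Followed as written, the SAP would leave protocol-defined events, including serious ones, out of the by-arm ocular adverse event, serious event and adverse-event discontinuation tables. It should be corrected.

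Confidence is high on the textual conflict and lower on its consequences. The harm is limited by the recording, notification and disposition provisions that remain, and by the listings if the sentence concerns tabulation only. The number of affected events is unknown. The conclusion assumes that no redacted passage supplies an exception.

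**What to change.** Reconcile Protocol 9.1 and SAP 17.1 so that both give the same answer for a worsening of dry eye. If an exclusion is kept because the CAE is meant to provoke symptoms:

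- list it in SAP Section 2 as a departure from the protocol;
- state that it limits tabulation and not recording, and confirm to sites that Protocol 9.1 and 8.4 apply if there is any sign that the sentence has been used in collection;
- fix the excluded terms before unmasking, including how they are separated from instillation-site events;
- keep serious events and events leading to discontinuation in the main tables;
- tabulate the excluded events separately by arm.

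The cost is one revised SAP sentence, one Section 2 entry, a short term list and one additional table, plus a site clarification if needed. The downside is that ocular adverse event counts may look slightly less favourable.

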10.9 Safety Variables

Adverse events will be coded using the MedDRA dictionary.

Frequencies and percentages will be provided per treatment arm of subjects with treatment-emergent adverse events (TEAEs), serious TEAEs, and TEAEs causing premature discontinuation. An adverse event is treatment-emergent if the adverse event occurs or worsens after the first dose of randomized treatment. Furthermore, frequencies will be given of subjects with TEAEs by system organ class, by system organ class and preferred term, by system organ class, preferred term and maximal severity, by system organ class, preferred term and strongest relationship, and by system organ class, preferred term, maximal severity, and strongest relationship. Separate analyses will be performed for ocular specific and all adverse events (including systemic).

Other safety endpoints, including visual acuity, slit lamp examination, and intraocular pressure, will be summarized by treatment arm and visit using descriptive statistics. Changes or shifts from baseline will also be summarized where appropriate. For assessments performed by eye, eyes will be summarized separately.

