5.1 General Trial Design

ADX-102-DED-032 is a randomized, double-masked, vehicle-controlled, parallel-group clinical trial to assess efficacy and safety of reproxalap compared to vehicle in subjects with dry eye disease. The clinical trial will consist of 3 visits to the clinic over a period of approximately two weeks. Visit 1 will consist of screening and pre-CAE baseline (specific to Visit 1) assessments with response to vehicle in the CAE. Randomization will occur at Visit 2. Prior to randomization at Visit 2, a pre-dose baseline (specific to Visit 2 and Visit 3) assessment will be collected. After randomization at Visit 2, subjects will be administered four doses of randomized treatment outside the CAE. Visit 3 will consist of response to randomized treatment in the CAE. Statistical analyses are tailored to evaluate the impact of reproxalap under conditions that *facilitate* dry eye symptoms through the presence of the CAE (Visit 1 and Visit 3), and are designed to accommodate various sources of pre-specified variation such as time of collection, to provide error variation, and to provide within-subject statistical testing across repeated measures.

Trial visits will be referred to in all tables and listings as the scheduled Visit. The following table shows the scheduled trial visits, the planned trial day (note that there is no Day 0, and that Day 1 corresponds to the day of randomization), and the acceptable visit window for each trial visit.

Scheduled Visit	Planned Trial Day	Visit Window	Visit Description
Visit 1	Day -14	-14 TO -16	Screening/CAE vehicle treatment visit
Visit 2	Day 1	N/A	Randomization/outside of CAE treatment visit
Visit 3	Day 2	N/A	CAE randomized treatment (reproxalap or vehicle) visit

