9.3 Partial or Missing Dates

The following conventions will be used to impute missing portions of dates for adverse events and concomitant medications, if warranted. Note that the imputed values outlined here may not always provide the most conservative date. In those circumstances, the imputed value may be replaced by a date that will lead to a more conservative analysis.

A. Start Dates

- 1) If the year is unknown, then the date will not be imputed and will be assigned a missing value.
- 2) If the month is unknown, then:
 - i) If the year matches the first dose date year, then impute the month and day of the first dose date.
 - ii) Otherwise, assign 'January.'
- 3) If the day is unknown, then:
 - i) If the month and year match the first dose date month and year, then impute the day of the first dose date.
 - ii) Otherwise, assign the first day of the month.

B. Stop Dates

- 1) If the year is unknown, then the date will not be imputed and will be assigned a missing value.
- 2) If the month is unknown, then assign 'December.'
- 3) If the day is unknown, then assign the last day of the month.

Unless having an end date before the first administration of the study drug, an adverse event with a completely missing start date will be interpreted as started between the first dose date included and

recovery to a satisfactory state, or stabilization, or appropriate outcome is established as judged by the Investigator (included), or the analysis cut-off date included, whichever comes first.

A medication with a completely missing start date will be interpreted as started before the first dose date. A medication with a completely missing end date will be interpreted as ongoing at the time of data extraction (and therefore being not stopped before the first dose).

10. Analysis Populations

Analysis populations include the ITT population, the per-protocol (PP) population, and the safety population. The statistical analysis of safety data will be performed on the safety population. The analysis of efficacy data will be performed on the ITT population, and, separately, on the PP population as a sensitivity analysis.

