15.2 Treatment Exposure

Extent of treatment exposure for subjects will be calculated in days using the following:

$$\text{Extent of Exposure (days)} = \text{Date of completion/discontinuation} - \text{date of Visit 1} + 1$$

Extent of treatment exposure for subjects who were lost to follow-up will be calculated in days using the following:

[figure not shown]
[figure not shown]
$$\text{Extent of Exposure (days)} = \text{Date of last recorded visit} - \text{date of Visit 1} + 1$$

The presentation of extent of treatment exposure will use the safety population. A subject listing of treatment exposure will also be produced that will include overall exposure. Descriptive statistics for exposure will be presented by treatment arm for overall exposure, exposure prior to Day 1 and exposure after Day 1.

16. Efficacy Analyses

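### The SAP's treatment-emergent start point, the first dose of an undefined *study treatment*, can be read to include the pre-randomization Visit 1 vehicle doses, whereas the protocol starts at the first randomized dose

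*SAP*

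**What the plan says.** The two definitions differ in one word that matters here.

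- Protocol 10.9: "An adverse event is treatment-emergent if the adverse event occurs or worsens after the first dose of randomized treatment".
- SAP 17.1: "Treatment-emergent adverse events (TEAEs) are defined as any adverse event that occurs or worsens on or after the first dose of study treatment".

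SAP 17.1 adds a companion rule: "Adverse events recorded in the eCRF which began prior to treatment will not be included in the summary tables". Such events go to listings only. SAP 9.3 uses a further unanchored term. For a partial adverse event start date in the matching year, the rule is to "impute the month and day of the first dose date".

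On precedence, the SAP introduction says that where directives differ "the SAP will supersede the protocol". SAP section 2 declares no deviation and describes its analyses as compatible with the protocol.

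Protocol 7.1.3 gives two vehicle doses at Visit 1, four randomized doses at Visit 2 and two at Visit 3. CAE exposures take place at Visits 1 and 3. Protocol 9.1 collects adverse events from consent, so events in the run-in reach the database. SAP 17.1 tabulates adverse events and TEAEs by treatment arm.

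**The concern.** In many trials the first dose of study treatment and the first randomized dose are the same event, and the wording would not matter. Here a vehicle run-in with a full CAE challenge comes before randomization, so the two phrases can point to dates about two weeks apart.

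TEAE tables by arm are the main safety output. If the start point is taken as Visit 1, a reaction to vehicle or to the CAE in a subject later assigned to reproxalap appears in the reproxalap column, although that subject had received no reproxalap. The same happens in the vehicle arm. Both rates rise, and the comparison carries events that randomized treatment cannot have caused. A real tolerability difference, for example at the instillation site, would then look smaller in relative terms.

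**Working it through.** **Step 1. What does *study treatment* cover?** The SAP gives no definition, so the surrounding text has to decide.

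Toward Visit 1:
- SAP 5.1 describes Visit 1 in its visit table as a "Screening/CAE vehicle treatment visit".
- SAP 15.2 computes the extent of treatment exposure from the date of Visit 1 and summarizes by arm "overall exposure, exposure prior to Day 1 and exposure after Day 1".
- Protocol 7.1, whose title is study treatments, contains the Visit 1 vehicle doses (7.1.3).
- SAP 5.1 writes of randomized treatment where it means that. SAP 17.1 does not.

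Toward Visit 2:
- SAP section 6, on study treatments, describes only randomized assignment.
- The protocol synopsis separates Visit 1 vehicle from test article, which starts at Visit 2.
- SAP 15.1 speaks of a two-day trial, which fits Days 1 and 2.
- SAP 17.1 ties study drug to the investigational drug.

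Both readings are open. SAP 15.2 is the strongest support for Visit 1, because it supplies a ready-made treatment start date that a programmer could reuse.

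**Step 2. What does a Visit 1 anchor add?** Counts from Protocol 7.1.3 and 8.3.1:

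| Anchor | Doses in window | CAE exposures in window |
|---|---|---|
| First randomized dose (Visit 2) | 4 + 2 = 6 | 1 |
| First vehicle dose (Visit 1) | 2 + 4 + 2 = 8 | 2 |

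The added, pre-randomization part is 2/8 = 25% of doses and 1/2 = 50% of CAE exposures.

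In calendar time, with no Day 0 and Visit 1 on Day -d, the window to Day 2 is d + 2 days, of which d precede randomization. At Day -14 this is 14/16 = 88%. The SAP's own window, Day -14 to Day -16, gives 14/16 to 16/18, or 88% to 89%. The protocol window, Day -12 to Day -30, gives 12/14 to 30/32, or 86% to 94%.

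**Step 3. Effect on rates (illustration only).** The documents give no run-in or on-treatment adverse event rates, so all rates here are assumed. Let q be the proportion with a run-in event, independent of later events, and p the proportion with an event in the randomized period. The tabulated rate becomes 1 - (1 - p)(1 - q), and the risk difference becomes (1 - q) times its former value. With p = 30% on reproxalap and 10% on vehicle:

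| q | Reproxalap | Vehicle | Difference | Risk ratio |
|---|---|---|---|---|
| 0 | 30% | 10% | 20 points | 3.0 |
| 5% | 33.5% | 14.5% | 19 points | 2.3 |
| 10% | 37% | 19% | 18 points | 1.9 |
| 20% | 44% | 28% | 16 points | 1.6 |

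With about 55 subjects per arm (Protocol section 4), the expected number of reproxalap subjects with a run-in event is 55q: 2.75, 5.5 and 11 for q = 5%, 10% and 20%. The chance of at least one is 1 - (1 - q)^55: 94%, 99.7% and over 99.9%.

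**Step 4. Date imputation.** An adverse event with a missing day or month may be assigned the first dose date under SAP 9.3. That is Visit 1 or Visit 2 depending on the reader, and the choice can decide whether the event is treatment-emergent.

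**The case against.** The strongest reply is that nothing here is a true conflict. An undefined SAP term that can be read in line with the protocol should be read that way, particularly as SAP section 2 claims compatibility. The precedence rule applies only to discrepant directives, so it does not make a Visit 1 anchor binding. This stands. A reader might infer that the SAP definitely starts the clock at Visit 1, but the visible text does not say so. SAP 11.3 on baseline definitions is redacted and cannot be checked.

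It can also be argued that separate adverse event and TEAE tables make sense only with a Visit 2 anchor, since consent and the first vehicle dose fall at the same visit. This carries some weight but does not settle the matter. SAP 17.1 also removes events that began before treatment from the summary tables, so read literally the two sets nearly coincide under either anchor.

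Two further inferences fail. One is that the wording biases the tables against reproxalap. Run-in events precede randomization and fall on both arms equally in expectation, so the result is inflation and dilution. The other is that 86% to 94% of TEAEs would come from before randomization. Those are shares of calendar days, most without dosing or a CAE. The exposure shares in Step 2 are the better guide.

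Finally, safety is summarized descriptively, and the absolute difference shrinks only by the factor 1 - q. Both are true and limit the importance of the point. They do not remove the ambiguity.

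**Conclusion.** The concern holds as an ambiguity with a real consequence. The SAP's TEAE start point can be read as Visit 1, its wording departs from Protocol 10.9, and no departure is declared. On the Visit 1 reading, events following 2 of 8 doses and 1 of 2 CAE exposures enter the TEAE tables by arm although they precede randomization. In expectation the rates rise about equally in both arms and the contrast is diluted.

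The effect on counts cannot be sized from the documents. The risk ratios above rest on assumed rates and on independence of run-in and later events, and show direction and rough scale only. Partial dates may be few, so the imputation issue is probably small in practice. The primary efficacy analysis is not affected. The change should be made because it is cheap and it protects the main safety tables.

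**What to change.** 1. In SAP 17.1, define a TEAE as an event that starts or worsens on or after the first dose of randomized treatment at Visit 2 (Day 1), consistent with Protocol 10.9.
2. Use that same date for the *prior to treatment* exclusion in SAP 17.1 and for *first dose date* in the adverse event date imputation of SAP 9.3.
3. Report events from Visit 1 up to that dose separately as run-in (vehicle CAE) events.

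If a Visit 1 start is in fact intended, SAP section 2 should declare it as a deviation from Protocol 10.9 and give the reason.

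The cost is a few words, one derivation date and one extra run-in listing or table. No new data are needed, since adverse events are collected from consent and Protocol 8.3.1 lists an adverse event query at Visit 2 ahead of randomization. The change should be made before unmasking.
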